1.2 Rationale

- There have been two retrospective studies that have investigated the safety and efficacy of 5-FU injected in periorbital skin grafts with or without Kenalog. The first (Massry 2011) used post-operative injections of a 50:50 mixture of 5-FU and triamcinolone for correction of medial canthal webs. In 2 patients, they found it to be safe and effective. The author noted he has used it previously for other scar management cases and was “very pleased with the results and [had] negligible side-effect[s].” The same author performed another study using 5-FU for skin grafts. This study evaluated 19 patients who had skin grafts for various purposes and were injected following surgery (similar to our protocol). This study demonstrated safety of the injection, with no cases of complication. The author concluded that the 5-FU is effective with “minimal scarring, high patient and surgeon satisfaction, and few complications
- Medication will be injected in the periocular skin graft area 2-3 weeks after surgery. The medication will be injected every 2-3 weeks for a total of up to four injections. Concentration of medication is 50mg/ml. Medication will be administered using a 1cc syringe with a 30gauge needle.

- Any competent patient (male or female) from the age of 18 to 89 that presents with any periocular pathology that requires skin graft for reconstruction and consents to participate will be a candidate to be included in the study.
- To your knowledge 5-FU hasn't been withdrawn from research or market in any country for any reason related to its safety or effectiveness.

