3. STUDY DESIGN

3.1 Study Design Description

- Randomized double blinded study comparing 5-FU versus placebo.
 - Patients will be randomized between treatment and control group. Double-masked study, neither patient nor physician providing treatment will know which group they are participating. Pharmacy will provide medication (5-FU versus saline).
 - Subject will be evaluated on first visit for the periocular pathology referred to our clinic requiring a full thickness skin graft to reconstruct the affected area. On that same visit patient will be scheduled to have surgery and research study will be presented. Whether or not patients decide to participate on study, surgery will be performed as normal. Then patient will be seen one week post-op as all surgical patients are normally seen. If patients decide to participate, 1-2 weeks later will start injecting medication (5-FU versus saline) on affected area. Injections will be repeated three more times, for a total of up to four, in a period of 2-3 weeks between each injection. After last injection is placed, patient will be seen 2-3 weeks after, and then 6 and 12 months after original surgery date. During each visit after surgery patient will be required to fill a scar assessment questionnaire.

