5. STUDY DRUG(S)/DEVICE(S)

5.1 Study Drug Information

- Study drug that will be administered to fifteen of our patients is 5-Fluorouracil, FDA-approved systemic chemotherapy medication to treat certain cancers, the concentration 50 mg/ml and will inject less than 1cc total in the subcutaneous tissue of the affected area.
- Study placebo that will be administered to the other fifteen of our patients is sodium chloride 0.9% (PF).
- Medications will be given every 2 to 3 weeks for a total of 4 injections.
- The amount of medication injected will depend on the extension/dimension of the periocular area affected with a maximum dose of 1cc total.

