8. SAFETY AND EFFECTIVENESS ASSESSMENTS

8.1 Safety Assessments

- Patients will be asked in each visit after surgery for any adverse events or complain from surgery or injection. It will be documented in the record as normally done with any patient.
- The PI will be responsible for safety review. Physician may withhold any injection if there is an adverse event like infection

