### 10.4 Analysis Population (if applicable)

- Independent sample t-test will be applied to the primary outcome analysis (i.e., comparison of mean changes in graft size from pre-treatment to the last follow up). In addition, for the secondary outcome we will utilize repeatedly measured POSAS scores over time by using longitudinal linear mixed effects model which can further determine the time dependency of the treatment effect. The model will include treatment group (group 0 for placebo and 1 for treatment), time (0=two-three weeks post-op visit / first injection, 1=second injection, 2=third injection, 3=fourth injection, 4=two to three weeks after last injection), and group x time. Both effects (1. group difference in the pre-treatment measurement 2. time trend of the control) will be considered fixed effects and the individual 2-3 weeks post-operative measurement random. Group x time effect is expected to be an increased slope of the treatment group over time. For the other outcome measurements, we will apply the same methods. Also statistical methods will include intention to treat (ITT) analysis to compare all subjects in the groups randomly assigned. We will exclude anyone who gets partial treatment, exit early or is lost to follow up; in those cases we will replace patient with another subject that meets the criteria. Discussed with [name] at MGH biostatistics.

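### The POSAS slope is fitted on injection-visit codes instead of elapsed weeks; actual weeks would remove an avoidable source of noise and, if visit timing differs by arm, of false slope

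*SAP*

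**What the plan says.** SAP 10.4 specifies a linear mixed model for POSAS with treatment group, time and their interaction. Time is "time (0=two-three weeks post-op visit / first injection, 1=second injection, 2=third injection, 3=fourth injection, 4=two to three weeks after last injection". No elapsed-time variable is named. The interaction is to be read as a slope: "Group x time effect is expected to be an increased slope of the treatment group over time".

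The schedule behind the codes is elastic. Protocol 1.2 states "The medication will be injected every 2-3 weeks for a total of up to four injections" and Protocol 3.1 states "Injections will be repeated three more times, for a total of up to four, in a period of 2-3 weeks between each injection". Protocol 5.1 gives a fixed number: "Medications will be given every 2 to 3 weeks for a total of 4 injections". Protocol 8.1 adds "Physician may withhold any injection if there is an adverse event like infection", and Protocol 7.7 says much the same.

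On who is analysed, SAP 10.4 says "Also statistical methods will include intention to treat (ITT) analysis to compare all subjects in the groups randomly assigned" and then "We will exclude anyone who gets partial treatment, exit early or is lost to follow up", with replacement. The 6- and 12-month questionnaires in Protocol 7.5 and 7.8 have no time code. SAP 10.5 names a t-test for the primary and secondary endpoints, which does not match the mixed model in 10.4.

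**The concern.** A slope on codes 0 to 4 treats each step as the same amount of time. The schedule does not make the steps equal, so scars of different ages share a code.

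The length of a gap is also settled after randomisation. Infection appears among the treatment-related events (Protocol 2.2 and 9.1) and is the protocol's own example of a reason to withhold an injection. If such events were commoner in one arm and stretched its gaps, that arm would gain more natural scar change per code. The model would report this as a difference in slope with no drug effect behind it. At stake is the interpretation of group x time for POSAS, and possibly for other outcomes, because SAP 10.4 extends the same methods to them.

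**Working it through.** **Stated figure.** The plan gives no sample size or power for the POSAS model. Its only figure is for graft size (SAP 10.3: difference 13.2%, SD 10%, two-sided alpha 0.05, 80% power, 20 in total). This reproduces: 2 x [10 x (1.960 + 0.842)/13.2]² = 9.01, so 10 per arm, with exact t-test power of 79.7%. The checks below use 10 per arm and the planned maximum of 15.

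**Visit windows.** The first injection is 2-3 weeks after surgery and each gap is 2-3 weeks (Protocol 1.2, 7.8). For code k, the earliest week is 2 + 2k and the latest is 3 + 3k.

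| Code | Weeks after surgery, full course |
|---|---|
| 0 | 2-3 |
| 1 | 4-6 |
| 2 | 6-9 |
| 3 | 8-12 |
| 4 | 10-15 |

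Code 4 spans 5 weeks, and neighbouring codes meet or overlap from code 1 onwards.

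**Size of a false slope.** Suppose scores change by b per week in both arms and the drug has no effect. The slope per code in an arm is b x (mean gap in that arm), so the false group x time slope is b x (difference in mean gap). The documents give neither quantity. Assume b of 0.1 to 0.3 within-patient SD per week:

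- 0.2-week difference: 0.02 to 0.06 SD per code, or 0.08 to 0.24 SD over the four steps.
- 0.5-week difference: 0.05 to 0.15 SD per code, or 0.2 to 0.6 SD over the four steps.

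A simulation on another scale (assumed trends of -0.5 and -1.0 points per week, residual SD 2, between-patient slope SD 0.2 points per week) confirms the formula. For a 0.5-week difference it predicts -0.25 and -0.50 per code; the simulated values were -0.255 and -0.492.

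**Type I error for group x time.** Null simulations with five visits per patient and trends of 0.1, 0.2 and 0.3 SD per week:

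| Mean gaps in the two arms | Codes, 10 per arm | Codes, 15 per arm | Actual weeks |
|---|---|---|---|
| Equal | about 5% | about 5% | about 5% |
| 0.2 week apart, overlapping | 5-7% | 6-8% | about 5% |
| 2.75 v 2.25 weeks, non-overlapping | 6%, 10%, 19% | 8%, 15%, 23% | 4-5% |

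Reruns of the last row moved by up to 3 points; at the steepest trend they gave 16-18% and 23-25%. With a between-patient slope SD of 0.1 per week, the worst cases fall to 12% and 16%. A 0.1-week difference leaves the error at about 5%.

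**Power.** With equal gaps, actual weeks gained 0-4 points of power over codes under the same trends.

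**Shortened course, only if such patients are analysed.** After two injections, the visit that follows the last one falls at 2 + 2 + 2 = 6 to 3 + 3 + 3 = 9 weeks. That is the window of code 2, but the definition of code 4 would place it two steps later. On the points scale above, if 20% of the treated arm stopped after two injections and were kept, the false slope is +0.14 to +0.25 per code (type I error 7-8%). At 50% it is +0.34 to +0.66 (15-32%). The sign is opposite to that of longer gaps. With weeks, type I error stays at 4.5-5.5%.

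**The case against.** The strongest reply is that nothing in the documents makes timing differ by arm. Both arms share one schedule, and patient and treating physician are masked (Protocol 3.1). The protocol speaks of withholding injections, not of delaying them, and Protocol 9.3 keeps patients with minor events on treatment. With equal gaps the codes hold the error rate. This largely stands. Masking does not rule out differences driven by reactions, and a patient whose injection was postponed and then given would complete the course and remain in the analysis. But this is a possible mechanism, not a documented one.

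The 0.5-week scenario is also extreme. Every gap in one arm is 2.5-3.0 weeks and every gap in the other 2.0-2.5, and the steepest trend implies a change of 0.3 x 4 x 2.5 = 3 SD over the course. This stands, so those rates are an upper illustration.

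A reader might infer that patients stopped after two injections will be modelled as if they had reached code 4, so that fewer injections in one arm will appear as a treatment slope. The documents do not support this as it stands. SAP 10.4 excludes partial treatment, Protocol 13.1 replaces part-treated subjects, and Protocol 9.3 leaves adverse-event withdrawals out of the analysis. The route opens only if the intention-to-treat sentence prevails, or if a course with an upper limit of four counts as complete with fewer.

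Finally, injection number is a defensible per-dose scale. That is fair, but a per-dose scale does not separate dose from scar age when the gaps vary.

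**Conclusion.** The point holds as an inexpensive improvement to a secondary analysis. The time codes are not elapsed time, and one code covers up to 5 weeks of scar age in a full course. With similar gaps in the two arms, the consequence is slight noise (0-4 points of power). With a 0.2-week difference in mean gap, type I error is about 5-8%; only an extreme, non-overlapping 0.5-week difference takes it to about 6-23%.

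These sizes rest on assumed linear trends of 0.1-0.3 SD per week, on assumed gap differences, and on time being fitted as a linear term. The SAP implies linearity by speaking of a slope but does not state it. The direction is not fixed: longer gaps and early stopping push the slope in opposite ways. It would go too far to say that the POSAS result will be biased towards 5-FU. The primary graft-size comparison is a t-test and does not use these codes.

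**What to change.** - In SAP 10.4, replace codes 0-4 with actual weeks from the visit date for every POSAS score, counted from surgery or from first injection. State the origin and estimate group x time on that scale. State that time is linear, and whether this is still assumed once the 6- and 12-month scores, which now have no time value, are included.
- Report visit timing and number of injections by arm.
- Reconcile, within SAP 10.4, the intention-to-treat sentence with the exclusion of partial treatment. Reconcile the upper limit of four injections in Protocol 1.2 and 3.1 with the fixed four in Protocol 5.1. Until then it is not settled whether patients with shortened courses enter the model.
- Reconcile SAP 10.4 with 10.5 on whether the mixed model or a t-test is the POSAS analysis.

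The coding change is one sentence in the SAP. It needs the visit date for each questionnaire; Protocol 12.1 does not list the CRF fields, so confirm that the date is recorded. The downside is negligible: the slope is per week instead of per injection.

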7.5 Follow-up Procedures

- After patient receives last injection, he will be followed 3 more times (2-3 week after last injection, and 6 and 12 month post-op from original surgery date). During those visits, patient will be required to fill out a questionnaire and will obtain a physical examination by the physician and photos will be taken.

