7.8 Schedule of Activities (Study Table)

	Intervention (injection)	Physical examination	Questionnaire	Photograph
Initial evaluation (screening)		X		X
Surgery				X
First post- operative visit		X		X
2-3 weeks after surgery (1 st injection)	X	X	X	X
2-3 weeks after 1 st injection (2 nd injection)	X	X	X	X
2-3 weeks after 2 nd injection (3 rd injection)	X	X	X	X

2-3 weeks after 3 rd injection (4 th injection)	x	x	x	x
2-3 weeks after 4 th injection		x	x	x
6 months after initial surgery		x	x	x
12 months after initial surgery		x	x	x

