8.2 Effectiveness Assessments

- Effectiveness of the study medication will be evaluated by measuring skin graft in each visit after surgery. The measurements will be recorded and analyzed at the end of the study to evaluate the graft size change during the whole study and compare the two groups. Photos will be taken also to objectively observe and document changes. Scar assessment will be evaluated with the use of a questionnaire completed by the observer/surgeon and patient. Questionnaire will be stored and at the end of the study values will be analyzed.

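### The POSAS mixed model in SAP 10.4 stops shortly after the injection course and leaves out the 6- and 12-month questionnaires, and its slope is not ranked against the t-test in 10.5

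*SAP*

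**What the plan says.** SAP 10.4 first assigns a t-test to the primary outcome, described as a "comparison of mean changes in graft size from pre-treatment to the last follow up". It then turns to POSAS: "In addition, for the secondary outcome we will utilize repeatedly measured POSAS scores over time", by a linear mixed model "which can further determine the time dependency of the treatment effect". The model has group, time and group by time, with the patient's pre-treatment level as the random term. Time is coded 0 at the first injection, then "1=second injection, 2=third injection, 3=fourth injection, 4=two to three weeks after last injection". A steeper slope in the treated group is expected.

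Protocol 7.5 schedules three visits once injections end: "2-3 week after last injection, and 6 and 12 month post-op from original surgery date". It requires a questionnaire at each. The table in 7.8 marks the questionnaire in the rows "6 months after initial surgery" and "12 months after initial surgery". On what becomes of the scores, Protocol 8.2 says only: "Questionnaire will be stored and at the end of the study values will be analyzed".

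SAP 10.5 refers back to the preceding text and gives a t-test at the 0.050 level for primary and secondary endpoints alike. It states no visit or contrast for POSAS.

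**The concern.** The time codes form a closed list, and the list ends before the two latest questionnaires. A model meant to describe how the treatment effect depends on time would then see only the injection course and the visit just after it. Patients would supply late scores that have no term in the only POSAS-specific analysis in the SAP. The primary outcome runs to the last follow-up, so the two results could describe different periods.

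A second question follows. If the slope in 10.4 and the t-test in 10.5 are both available for POSAS and neither leads, the choice between them can be made after the data are seen.

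**Working it through.** The plan gives no sample size, power, variance or correlation for POSAS, so it has no POSAS figure to reproduce. The check is a count, a timeline and two calculations on stated assumptions.

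**Questionnaires (Protocol 7.8).** Four injection visits + one post-course visit + 6 months + 12 months = 7. Codes 0-4 in 10.4 cover 5, so 7 − 5 = 2 have no term. (Protocol 3.1 asks for a questionnaire at every visit after surgery, which would add the first post-operative visit. That is a separate mismatch with 7.8.)

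**Timeline.** Inputs are a first injection 2-3 weeks after surgery and 2-3 weeks between later visits (Protocol 1.2, 3.1, 7.8), with all four injections given.
- Code 4 falls 5 × 2 = 10 to 5 × 3 = 15 weeks after surgery.
- From first injection, code 4 is at 4 × 2 = 8 to 4 × 3 = 12 weeks.
- Taking 12 months as 52.2 weeks, the last visit is 52.2 − 3 = 49.2 to 52.2 − 2 = 50.2 weeks from first injection.
- Share covered: 8/50.2 = 16% to 12/49.2 = 24%.
- Gaps after code 4: to 6 months, 26.1 − 15 = 11 to 26.1 − 10 = 16 weeks; from 6 to 12 months, 26 weeks. Between the coded visits the gap is 2-3 weeks.

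**Slope and t-test.** Side by side, 10.4 supplies a model, a contrast (group by time) and a span of visits for POSAS. Section 10.5 supplies a t-test for secondary endpoints without a POSAS visit. Section 10.4 also says other outcomes get the same methods, but does not say which method leads.

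**Covariance.** A random patient level alone implies equal correlation between all visits. Simulated trials with no treatment effect (40,000 per setting, 10 or 15 per arm) show how much this matters for the existing five-visit slope test at 0.05:
- Equal correlation (0 to 0.9 assumed): the slope test rejects in about 5%. The slope test or a t-test of change to 12 months rejects in about 9%.
- Correlation decaying with time (assumed 0.5 to 0.95 per 2.5 weeks): the slope test alone rejects in about 14-22%, and either test in about 17-25%.
- With a t-test on each patient's own slope in place of the random-intercept model, the either-test figure stays near 9% under decay.

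The either-test figures matter only if either result could be claimed.

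**Precision of a 12-month contrast.** Take the score SD as 1 and assume correlation r = 0.5 with the first-injection score.
- Difference in change: SD = √(2(1 − 0.5)) = 1. The 95% half-width is t × √(2/n): 2.101 × √(2/10) = 0.94 SD at 10 per arm, and 2.048 × √(2/15) = 0.75 SD at 15.
- Baseline-adjusted: SD = √(1 − 0.25) = 0.866. Half-width is 2.110 × √(2/10) × 0.866 = 0.82 SD at 10, and 2.052 × √(2/15) × 0.866 = 0.65 SD at 15.

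**The case against.** The best defence is that the model is a supplement. Section 10.4 introduces it as an addition to the t-test, and 10.5 refers back when it gives secondary endpoints a t-test. On that reading a POSAS change-to-last-follow-up t-test leads and uses the 12-month score, and the model only describes the injection course. The reading is plausible, and it limits the point: what the model cannot show is not the same as what the whole plan cannot show. It does not remove the point. The contrast it relies on is worded for graft size, and the 6-month score has no place on this reading either.

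A reader might infer that the plan ignores the late scores altogether. The documents do not support that: Protocol 8.2 says questionnaire values will be analysed, and 10.5 may cover month 12. A reader might also infer that the SAP names no POSAS contrast. It does name one, the group-by-time slope with an expected direction. What is missing is its rank against the t-test.

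Finally, POSAS is secondary, so the rejection rates above are not an error rate for the trial's main conclusion.

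**Conclusion.** The omission of the 6- and 12-month scores from the mixed model is literal and held with high confidence: 2 of 7 scheduled questionnaires, and all but the first 16-24% of the time from first injection to month 12. The percentages assume four injections at the stated intervals. As written, the model cannot distinguish a lasting difference from a fading or a late one.

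That the slope and the t-test are unranked is held with moderate confidence, because it turns on how the back-reference in 10.5 is read. On the reading most favourable to the plan, only the 6-month score goes unused.

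The simulated rates and half-widths rest on assumed correlations. They guide the fix and are not needed to establish the omission. The matter should be corrected, but it does not touch the primary test or the sample size.

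**What to change.** 1. In SAP 10.4, include the 6- and 12-month POSAS scores. Treat visit as a category, or time as actual weeks since first injection. Do not append codes 5 and 6 to the linear scale, because the late gaps are several times longer than the others.
2. Specify a within-patient covariance that does not force equal correlation across unequally spaced visits, or a random slope if time is in weeks. With about 10-15 patients per arm, keep the structure simple and state a small-sample degrees-of-freedom method.
3. Reconcile 10.4 and 10.5 before unmasking. Name one lead POSAS analysis with one scale (patient or observer), one contrast and one visit, for example the 12-month score adjusted for the first-injection score. Either method may lead. Label the rest supportive, and say where the 6-month score is used.

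The cost is SAP wording, with no new visits or data. With visit as a category, group by time has 6 terms instead of 1 slope, so the named contrast has to carry the conclusion. A straight line in weeks keeps one slope but assumes steady change over about 50 weeks and would not show fading. The 12-month contrast will be imprecise, so report it as an estimate with its 95% interval.

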3.2.1 Randomization Procedures

- Randomization will be performed by the research pharmacy per their protocol. The study will be conducted in a double-blind manner.

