### 10.3 Sample Size Determination

- The plan number of subjects to be enrolled into the clinical study is up to 15 for the treatment group and up to 15 for the placebo group. A total sample size of 20 patients is needed to achieve a 80% power to detect a difference of at least 13.2% less than the control in mean changes in graft size from pre-treatment (2-3 weeks post-operative date) to the last follow up with a standard deviation of 10% (common to both groups) and with a significant level (alpha) of 0.050 using a two-sided two-sample equal-variance t-test. If we take into account a 20% dropout rate out of 20 patients, then 12 patients are needed to be enrolled into each arm of the study. For that reason, 15 patients are going to be enrolled but statistical analysis can be done once 10 patients in each arm have completed the study. Determined with the help of [name] at MGH biostatistics department.

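### The POSAS mixed model is valid, but it estimates a pre-injection group difference that randomisation sets to zero in expectation, and so gives up some precision on the treatment slope

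*SAP*

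**What the plan says.** SAP 10.4 gives the only detailed specification of the POSAS analysis, a longitudinal linear mixed model: "The model will include treatment group (group 0 for placebo and 1 for treatment), time (0=two-three weeks post-op visit / first injection". Time runs over five visits, ending at "4=two to three weeks after last injection", and the third term is group x time.

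- **Fixed effects:** "Both effects (1. group difference in the pre-treatment measurement 2. time trend of the control) will be considered fixed effects".
- **Random effect:** "the individual 2-3 weeks post-operative measurement random", which is a patient-level random intercept. No random slope is mentioned.
- **Target:** "Group x time effect is expected to be an increased slope of the treatment group over time".

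Allocation is randomised and double-masked (Protocol 3.1). Protocol 3.2.1 states: "Randomization will be performed by the research pharmacy per their protocol". SAP 10.3 plans "up to 15 for the treatment group and up to 15 for the placebo group" and allows analysis once 10 per arm have completed. The schedule in Protocol 7.8 places the POSAS questionnaire and the first injection at the same visit.

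Two other statements bear on the point. SAP 10.4 names an ITT comparison but also excludes and replaces patients who are partly treated, leave early or are lost. SAP 10.5 names a t-test for both primary and secondary endpoints.

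**The concern.** With time coded 0 at the first-injection visit, the group main effect is the arm difference at that visit, and 10.4 describes it in those terms. No study drug has been given by then, provided the questionnaire precedes the injection. In a randomised comparison any difference is therefore chance.

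A free group term makes the group x time estimate a difference between within-patient slopes that takes no account of the chance imbalance at the start. A common time-0 mean uses that imbalance and estimates one parameter fewer. POSAS has no sample-size or power statement of its own, and the analysis may run on 10 patients per arm, so precision for this endpoint has no planned margin. SAP 10.4 also extends the same methods to the other outcome measurements.

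**Working it through.** **The plan's own figure.** SAP 10.3 sizes the trial on graft size: difference 13.2, SD 10, two-sided alpha 0.050, total 20. This reproduces: 10 per arm gives an exact t-test power of 79.7%, against the stated 80%. It says nothing about POSAS, for which the documents give no variance, correlation or power.

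**Inputs.** From SAP 10.4: visits t = 0, 1, 2, 3, 4; linear time; random intercept. From SAP 10.3: equal arms, n = 10 per arm. Assumed: within-patient correlation r, with total variance set to 1.

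**Slope variance with a free group term.** The sum of squares of t about its mean is Sxx = 4 + 1 + 0 + 1 + 4 = 10, so

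Var(free) = 2(1 − r)/(10n).

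At r = 0.5 and n = 10 this is 2 × 0.5/100 = 0.010, SE 0.100.

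**Slope variance with a common time-0 mean.** Here the sum of t² = 30 and the sum of t = 10. The information on the slope per arm is [30 − 100r/(1 + 4r)]/(1 − r), so

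Var(common) = (2/n)(1 − r)/[30 − 100r/(1 + 4r)].

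**Ratio.** Var(common)/Var(free) = 10/[30 − 100r/(1 + 4r)] = (1 + 4r)/(3 + 2r). At r = 0.5 this is 3/4 = 0.75.

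The last column takes a free model with 80% power and computes Φ(2.8016/√ratio − 1.96).

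| r | Ratio | Saving | SE free | SE common | Power if free model has 80% |
|---|---|---|---|---|---|
| 0.3 | 2.2/3.6 = 0.611 | 39% | 0.1183 | 0.0925 | 95% |
| 0.5 | 3.0/4.0 = 0.750 | 25% | 0.1000 | 0.0866 | 90% |
| 0.7 | 3.8/4.4 = 0.864 | 14% | 0.0775 | 0.0720 | 85% |
| 0.8 | 4.2/4.6 = 0.913 | 9% | 0.0632 | 0.0604 | 83% |
| 0.9 | 4.6/4.8 = 0.958 | 4% | 0.0447 | 0.0438 | 82% |

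At r = 0.5, 10 per arm with the common mean carry the information of 10/0.75 = 13.3 per arm without it.

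**If patient slopes vary.** Adding a random slope with SD 0.3 of the residual SD raises the ratios to 0.80, 0.87, 0.93, 0.95 and 0.98, so the savings fall to about 20%, 13%, 7%, 5% and 2%. With a slope variance of 10% of the total variance, the saving is 8% at r = 0.5 and 0.4% at r = 0.9.

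**Simulation.** REML fits with 10 per arm (300 runs) found both estimators unbiased under randomisation. The empirical SD of the slope was 0.093 free against 0.080 common at r = 0.5, and 0.061 against 0.060 at r = 0.8.

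**When the common mean does harm.** If the analysed arms differ systematically at time 0 by δ, the constrained slope is biased by δ(1 − r)/(3 + 2r). At r = 0.5 and δ = 0.5 total SD, the bias is 0.5 × 0.5/4 = 0.0625, or 0.0625/0.0866 = 0.72 SE. With no treatment effect and δ of 0.3 to 0.5 SD, the nominal 5% test rejects about 7–11% of the time at r = 0.5 and 10–18% at r = 0.3 (normal approximation). The δ values are assumptions.

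**The case against.** The strongest reply is that nothing is wrong: group, time and group x time with a random intercept is a standard, unbiased model, and POSAS is secondary with no power claim. That stands, and it limits the point to efficiency. It does not remove it, because the baseline score is already collected and the gain needs no further patients.

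The second reply is that the free group term protects against selection. SAP 10.4 excludes and replaces incomplete patients. Protocol 5.2 gives replacements for non-compliant patients the corresponding medication, and Protocol 9.3 leaves patients withdrawn for adverse events out of the analysis. In such a set the expected time-0 difference need not be zero, and the bias shown above is largest at low correlation, where the gain is also largest. This stands too: the constraint is sound only in the all-randomised set, which 10.4 also names.

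Three stronger readings are tempting, and the documents do not support them.

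- **That the plan ignores baseline POSAS.** It does not: baseline enters as the time-0 outcome, and the estimate is a five-visit slope rather than a simple change score.
- **That modelling post-injection scores with baseline as a covariate amounts to the same thing.** If group and group x time are kept over times 1 to 4, Sxx falls to 2.25 + 0.25 + 0.25 + 2.25 = 5. The slope variance then doubles under the random-intercept model.
- **That the gain is sure to be large.** No correlation is given, and at 0.8 to 0.9 the saving is about 2–9%.

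**Conclusion.** The point holds as a minor efficiency gain on a secondary endpoint. The saving in slope variance runs from 39% at an assumed correlation of 0.3 to 4% at 0.9 under the plan's own covariance, and is less with varying slopes. It rests on three conditions:

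- the analysis includes all randomised patients;
- the time-0 POSAS is completed before the first injection, an order that the documents do not state, although 10.4 treats the value as pre-treatment;
- the mixed model is the operative POSAS analysis, which SAP 10.5 leaves in doubt.

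A reader might infer that the planned POSAS result would be biased, or that the trial's sample size is affected. Neither follows: the planned model is valid under randomisation, and the graft-size t-test and its N do not depend on this choice.

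**What to change.** In SAP 10.4, before unblinding:

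1. For the all-randomised (ITT) set, drop the group main effect so that both arms share one time-0 mean. Keep time and group x time.
2. State that the time-0 POSAS is completed before the first injection.
3. Keep the model with a free group term as a sensitivity analysis, and do not apply the common-mean model to a set of completers and replacements.
4. Do not offer a post-injection model that retains both group and group x time as an alternative.
5. Reconcile SAP 10.5 with 10.4 on whether the mixed model or a t-test is the POSAS analysis, and settle the contradiction in 10.4 between ITT and exclusion with replacement.

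The cost is a few sentences and one extra model fit, with no new assessments. The risk to accept is bias if the time-0 means differ systematically in the set analysed, which items 1 and 3 are there to control.
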